6.12. Study Week 36 (Day 253)

The Study Week 36 visit must occur within ± 2 days of the scheduled date. During this visit, the following study procedures will be performed:

- A physical examination including body weight;
- Vital signs (temperature, sitting blood pressure, heart rate) after at least 3 minutes of rest;
- Blood samples will be collected for serum chemistry, hematology, serum pregnancy test (in women of childbearing potential), and PK measurements; the date and time of collection of the PK sample will be recorded;
- Biomarker plasma sample will be collected;
- The date and time of the last dose of study drug prior to collection of the PK sample will be recorded;
- A urine sample will be collected for urinalysis;
- The anatomic location and number of HS inflammatory nodules, abscesses, fistulae, and hypertrophic scars will be recorded;
- Follow-up photography of lesions will be completed;
- Compliance with daily recording of pain and study drug dosing in diaries will be checked and re-training provided, if necessary;
- Items for the Sartorius and modified Sartorius scores will be collected;
- IHS4 score will be calculated;
- The Investigator will complete the HS-PGA;
- Study personnel will record health-economic information;
- Subjects will be asked to complete the SF-36 v2, EQ-5D-5L, HiSQOL, DLQI, and WPAI:SHP forms;
- Drug accountability will be performed on the returned bottle(s) of study drug;
- Any changes in concomitant medication use will be recorded, including alcohol intake, recreational drug use, non-prescription medications, herbal preparations or special diets;
- Any adverse events will be recorded;
- After all study procedures have been completed, the subject will be reminded to:
 - Record severity of skin pain in daily diary;
 - Come to the study center for the Week 44 study visit; and
 - Continue taking all their other concomitant medications as usual.

6.13. Study Week 44 (Day 309)

The Study Week 44 (follow-up) visit must occur within ± 4 days of the scheduled date. During this visit, the following study procedures will be performed:

- A physical examination including body weight;
- Vital signs (temperature, sitting blood pressure, heart rate) after at least 3 minutes of rest;
- A 12-lead ECG will be taken to exclude any clinically significant findings;
- Blood samples will be collected for serum chemistry, hematology and PK measurements; the date and time of collection of the PK sample will be recorded;
- A urine sample will be collected for urinalysis;
- The anatomic location and number of HS inflammatory nodules, abscesses, fistulae, and hypertrophic scars will be recorded;
- Follow-up photography of lesions will be completed;
- Items for the Sartorius and modified Sartorius scores will be collected;
- IHS4 score will be calculated;
- The Investigator will complete the HS-PGA;
- Study personnel will record health-economic information;
- Subjects will be asked to complete the SF-36 v2, EQ-5D-5L, HiSQOL, DLQI, and WPAI:SHP forms;
- The completed daily diary will be collected;
- Any changes in concomitant medication use will be recorded, including alcohol intake, recreational drug use, non-prescription medications, herbal preparations or special diets;
- Any adverse events will be recorded;
- After all study procedures have been completed, the subject will exit the study.

6.14. Early Termination Visit

If a subject will be withdrawn early from the study, the following termination procedures must be completed whenever possible:

- A physical examination including body weight;
- Vital signs (temperature, sitting blood pressure, heart rate) after at least 3 minutes of rest;
- A 12-lead ECG will be taken to exclude any clinically significant findings;
- Blood samples for serum chemistry, hematology, and serum pregnancy test (in women of childbearing potential), and PK measurements; the date and time of collection of the PK sample will be recorded;
- Biomarker plasma sample will be collected;

- A urine sample will be collected for urinalysis;
- The anatomic location and number of HS inflammatory nodules, abscesses, fistulae, and hypertrophic scars will be recorded;
- Follow-up photography of lesions will be completed;
- Items for the Sartorius and modified Sartorius scores will be collected if the prior visit where this assessment was made was more than 2 weeks before;
- IHS4 score will be calculated;
- The Investigator will complete the HS-PGA, if the prior visit where these assessments were made was more than 2 weeks before;
- Study personnel will record health-economic information;
- Subjects will be asked to complete the SF-36 v2, EQ-5D-5L, HiSQOL, DLQI, and WPAI:SHP forms, if the prior visit where these assessments were made was more than 2 weeks before;
- Drug accountability will be performed on the returned bottles of study drug;
- Completed daily diary will be collected;
- Any changes in concomitant medication use will be recorded, including alcohol intake, recreational drug use, non-prescription medications, herbal preparations or special diets;
- Any adverse events will be recorded.

7. STUDY ASSESSMENTS

7.1. Efficacy Assessments

7.1.1. Location and Extent of Hidradenitis Suppurativa Assessment

The location and extent of HS will be assessed at visits in the [Time and Events Table](#) by recording the anatomic location(s) of the disease, as well as the number of HS inflammatory nodules, abscesses, fistulae, and hypertrophic scars in each of the locations in the EDC. All study Investigators will receive study specific training to assess HS lesions.

The same Investigator should assess the lesions at each visit to assure consistency. Study sites should schedule all visits for the same subject such that the same Investigator is available to assess the lesions of that subject.

The information regarding location and extent of HS involvement will be used to determine the Hurley Stage and also to calculate the HiSCR at post-baseline visits. The HiSCR will be calculated programmatically in the EDC.

7.1.2. Sartorius and Modified Sartorius Scores

Twelve body areas will be evaluated at visits specified in the [Time and Events Table](#) to calculate the Sartorius and modified Sartorius scores:

- left and right axillae,
- left and right inframammary areas,
- intermammary area,
- left and right buttocks,
- left and right inguino-crural folds,
- perianal area and perineal area, and
- other (specify).

A score of 4 indicates the least severe disease, and higher scores indicate increasingly severe disease. There is no upper limit in the score ([Sartorius et al, 2003](#); [Sartorius et al, 2009](#)).

The presence of nodules, abscesses, fistulae, hypertrophic scars, and other findings will be recorded in the EDC. The longest distance between two lesions and whether lesions are separated by normal skin will also be recorded.

7.1.3. International Hidradenitis Suppurativa Severity Score System

The International Hidradenitis Suppurativa Severity Score (IHS4) is simple to calculate and has been validated with the use of existing physician-derived outcomes such as HS-PGA, Hurley classification, MSS or Expert Opinion classification) and patient-reported outcome measure (DLQI). IHS4 score (points) = (number of nodules multiplied by 1) + (number of abscesses multiplied by 2) + [number of draining tunnels (fistulae/sinuses) multiplied by 4]. A score of 3 or less signifies mild HS, a score of 4–10 signifies moderate HS and a score of 11 or higher signifies severe HS.

7.1.4. Hidradenitis Suppurativa-Physician Global Assessment (HS-PGA)

The HS-PGA is an ordinal scale specific to HS that categorizes subjects into clear, minimal, mild, moderate, severe, or very severe disease, and it was used successfully in a phase 2 interventional clinical trial. A recently developed six stage PGA was defined as follows ([Kimball et al, 2012](#)):

- Clear: no inflammatory or non-inflammatory nodules
- Minimal: Only the presence of non-inflammatory nodules
- Mild: Less than 5 inflammatory nodules or 1 abscess or draining fistula and no inflammatory nodules
- Moderate: Less than 5 inflammatory nodules or one abscess or draining fistula and one or more inflammatory nodules or 2–5 abscesses or draining fistulae and less than ten inflammatory nodules
- Severe: 2–5 abscesses or draining fistulae and ten or more inflammatory nodules
- Very severe: More than 5 abscesses or draining fistulae

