4.1. Inclusion Criteria

Subjects must meet all of the following inclusion criteria in order to enter the study:

1. Aged at least 18 years of age;
2. Clinical diagnosis of HS (Hurley Stage II or III), confirmed by a dermatologist, for at least 6 months prior to Screening. Hurley Stage II disease is defined as having one or more widely separated recurrent abscesses with tract formation and scars; Stage III disease is defined as having multiple interconnected tracts and abscesses across an entire anatomical area with diffuse or near diffuse involvement;
3. HS lesions are present in at least 2 distinct anatomic areas (e.g., left and right axilla; or left axilla and left inguino-crural fold), one of which is Hurley Stage II or Hurley Stage III;
4. Inadequate or loss of response to a systemic course of antibiotics of 90 days. However, a subject who has completed less than 90 days of antibiotic treatment may be allowed into the study upon discussion with the Medical Monitor if: 1) the subject has demonstrated intolerance to or contraindication for antibiotics to treat HS, or 2) it was determined by the Investigator that an antibiotic course of at least 28 days to treat HS did not benefit the subject and a continued antibiotic therapy would therefore not be indicated.

Inadequate or loss of response is defined if the following was observed despite antibiotic treatment:

- a. Progression of Hurley Stage (i.e., the Hurley Stage of at least one affected anatomic region progressed from I→II, II→III, or I→III);
 - b. Subject required at least one intervention (e.g., incision and drainage or intralesional injection of corticosteroid);
 - c. Subject experienced pain interfering with activities of daily living, with unsatisfactory relief from over-the-counter analgesics (e.g., ibuprofen or acetaminophen);
 - d. Subject experienced pain requiring opioids, including tramadol;
 - e. Subject experienced drainage interfering with activities of daily living (e.g., requires multiple dressing changes and/or changes of clothes daily);
 - f. Subject experienced an increase in the number of anatomic regions affected by HS;
 - g. Subject experienced at least one new abscess or one new draining fistula.
5. Must have at least 5 inflammatory nodules or abscesses at Screening;
 6. Must agree to use a topical antiseptic daily over the course of the study; topical antiseptics may include but are not limited to chlorhexidine, triclosan, benzoyl peroxide, or diluted bleach in bath water;

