The proportion of subjects achieving NRS30 at Post Baseline visits will be calculated as those subjects having % Reduction from Baseline in NRS \geq 30 and (Baseline NRS - Post Baseline NRS \geq 1) at Post Baseline visits divided

by the total number of subjects having Baseline NRS ≥ 3 in each treatment group.

5) Proportion of subjects with baseline Hurley Stage II who achieved an abscess and inflammatory nodule count of 0, 1, or 2.

Please see the description of item 4) in Secondary Endpoints for details.

The proportion of subjects with baseline Hurley Stage II achieving AN count of 0, 1, or 2 at Post Baseline visits will be calculated as those subjects having baseline Hurley Stage II and AN Count = 0, 1, or 2 at Post Baseline visits divided by the total number of subjects having baseline Hurley Stage II in each treatment group.

6) Change from Baseline in the Sartorius score, modified Sartorius score, IHS4 score, and HS-PGA to quantify the severity change of HS.

Sartorius score, modified Sartorius score, and IHS4 score has been described in items 1) and 3) of Secondary Endpoints.

The Hidradenitis Suppurativa-Physician's Global Assessment (HS-PGA) is an ordinal scale specific to HS that categorizes subjects into clear, minimal, mild, moderate, severe, or very severe disease, and it was used successfully in a phase 2 interventional clinical trial. A recently developed six stage PGA was defined as follows:

Hidradenitis Suppurativa-Physician's Global Assessment		
Score	Short	Definition
	Descriptor	
0	Clear	0 abscesses, 0 draining fistulas, 0
		inflammatory nodules, and 0 non-
		inflammatory nodules
1	Minimal	0 abscesses, 0 draining fistulas, 0
		inflammatory nodules, and only presence of
		non-inflammatory nodules
2	Mild	0 abscesses, 0 draining fistulas, and 1 to 4
		inflammatory nodules
		or
		1 abscess or draining fistula (sum of
		abscesses and draining fistulas is 1) and 0
		inflammatory nodules
3	Moderate	0 abscesses, 0 draining fistulas, and ≥ 5
		inflammatory nodules
		or
		1 abscess or draining fistula and ≥1
		inflammatory nodule
		or

		2 to 5 abscesses or draining fistulas (sum of
		abscesses and draining fistulas is 2 to 5) and
		< 10 inflammatory nodules
4	Severe	2 to 5 abscesses or draining fistulas and ≥10
		inflammatory nodules
5	Very severe	>5 abscesses or draining fistulas (sum of
		abscesses and draining fistulas >5)

HS-PGA is collected from the "Hidradenitis Suppurativa-Physician's Global Assessment (HS-PGA)" CRF.

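### Protocol 7.1.4 misdefines HS-PGA: nodules-only disease fits two grades or none, and the SAP does not tie its sound table to the score recorded on the CRF

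*Protocol*

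**What the plan says.** Protocol 7.1.4 sets out six grades. Two of them begin with the same nodule limb:

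- The third grade on the list is printed as "Mild: Less than 5 inflammatory nodules or 1 abscess or draining fistula and no inflammatory nodules".
- The grade above it in severity is printed as "Moderate: Less than 5 inflammatory nodules or one abscess or draining fistula and one or more inflammatory nodules", followed by a third limb for 2 to 5 abscesses or draining fistulae with fewer than ten inflammatory nodules.

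The top two grades both require abscesses or draining fistulae. One is "Severe: 2–5 abscesses or draining fistulae and ten or more inflammatory nodules"; the other, at the end of the scale, is "Very severe: More than 5 abscesses or draining fistulae".

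The SAP (VIII.B, Other Efficacy Endpoints, item 6) prints a different table, with scores 0 to 5 and explicit zero counts. Its first Moderate limb reads "0 abscesses, 0 draining fistulas, and ≥ 5" inflammatory nodules. Directly below the table the SAP says that "HS-PGA is collected from the" dedicated HS-PGA CRF. The protocol's visit sections have the Investigator complete the HS-PGA.

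SAP I.A gives the SAP's statistical definitions precedence over the protocol's. SAP Section X, which lists changes from the protocol, does not mention HS-PGA. Inclusion criterion 5 (Protocol 4.1) is "Must have at least 5 inflammatory nodules or abscesses at Screening".

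**The concern.** The two documents define the same scale differently, and the protocol's version does not work as a classification. A table in an analysis plan does not alter a grade already recorded on a form at a site visit. If the form or the sites followed Section 7.1.4, precedence of SAP definitions would not by itself correct the data.

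HS-PGA is used in several places. It is a named objective against placebo (Protocol 2.2, item 5a), a baseline characteristic (SAP VII.C), and an endpoint analysed as change from baseline with a repeated-measures model (SAP VI.E). An ambiguous or missing grade at baseline or follow-up would carry straight into that change score.

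**Working it through.** No sample-size, power or alpha figure is involved. The check is whether each set of rules gives every lesion pattern exactly one grade.

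**Step 1: rules side by side.** Let n be inflammatory nodules and s be abscesses plus draining fistulae. The protocol column takes each *or* as separating a limb and takes the nodule-only limb to imply s = 0.

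| Pattern | Protocol 7.1.4 | SAP VIII.B |
|---|---|---|
| n = 1–4, s = 0 | Mild and Moderate | Mild (2) |
| n ≥ 5, s = 0 | none | Moderate (3) |
| n = 0, s = 1 | Mild | Mild (2) |
| n ≥ 1, s = 1 | Moderate | Moderate (3) |
| n < 10, s = 2–5 | Moderate | Moderate (3) |
| n ≥ 10, s = 2–5 | Severe | Severe (4) |
| s > 5 | Very severe | Very severe (5) |

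The second row has no protocol grade for a simple reason. Clear and Minimal exclude inflammatory nodules, the nodule limb of Mild and Moderate stops at 4, and every remaining limb needs at least one abscess or draining fistula.

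**Step 2: enumeration.** The grid takes n from 0 to 30, abscesses 0 to 8, draining fistulae 0 to 8, and non-inflammatory nodules absent or present: 31 × 9 × 9 × 2 = 5,022 combinations. Because the protocol wording is loose, it was coded under 2 × 2 × 2 = 8 readings: two and/or groupings, with or without an implied zero abscess and fistula count, and abscess and fistula numbers taken as a sum or as either count.

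- *Gap.* In all 8 readings the ungraded combinations are exactly n = 5 to 30 with no abscess and no draining fistula: 26 × 1 × 1 × 2 = 52.
- *Overlap.* In all 4 readings where each *or* separates a limb, 1 to 4 nodules alone are both Mild and Moderate. Under the reading tabulated above that is the whole overlap: 4 × 2 = 8 combinations. Without the implied zeros it widens to 5 × 81 × 2 = 810. Under the other, more strained grouping it disappears in one of 4 variants and moves to zero-nodule patterns in the other 3; the gap remains in all 4.
- *SAP table.* 0 combinations ungraded, 0 in more than one grade.

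These are counts of lesion patterns, not of subjects.

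**Step 3: reach.** Five or more inflammatory nodules with no abscess satisfy inclusion criterion 5. If there is also no draining fistula, the protocol gives no grade and the SAP gives Moderate. The fistula condition matters: 8 nodules, no abscess and 1 draining fistula is Moderate under both documents.

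**Step 4: effect on one subject.** Take 6 nodules at baseline and 3 at Week 12, with nothing else. Under the SAP table the change is 2 − 3 = −1. Under the protocol the baseline has no grade. If the investigator settles on Moderate at baseline, Week 12 may be Mild (2 − 3 = −1) or Moderate (3 − 3 = 0), so a one-grade improvement can be recorded as no change.

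**Step 5: can the SAP table be applied?** Inflammatory nodules, abscesses and fistulae are recorded at Day 1 and every later visit (Protocol Section 6). The SAP analyses inflammatory nodules, non-inflammatory nodules, abscesses and draining fistulae (III.A), which are all the counts its table needs. The protocol's visit lists do not name non-inflammatory nodules, but that count only separates Clear from Minimal.

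**The case against.** The strongest reply is that nothing shows a grade was ever assigned from the faulty text. The CRF is not among the documents and may already carry the SAP wording; the SAP table sits directly above the sentence naming that form. The visit sections do not send the Investigator to 7.1.4, although the Day 1 section cross-refers for the Sartorius and IHS4 scores. Investigators also receive study-specific training on lesion assessment (Protocol 7.1.1), whose content is not shown. This stands: a reader might infer that grades have already been recorded under the wrong definition, and the documents do not establish it.

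Second, SAP definitions supersede the protocol's and the counts exist, so the problem can be repaired. That also stands. A reader might infer that the SAP table cannot help because the score comes from a form; in fact a derivation is feasible. What remains is that the SAP does not plan one. By contrast, HiSCR is calculated programmatically (Protocol 7.1.1).

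Third, the reach may be small. Neither document gives the frequency of nodules-only disease without draining fistulae, and Hurley II and III are defined by abscesses with tracts, though that does not exclude the pattern at a given visit. Calling it common would have no source.

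Fourth, the stakes are low. HS-PGA is part of one other efficacy endpoint, outside the ranked sequence H2 to H9, and such comparisons are supportive or exploratory with no multiplicity adjustment (SAP VI.I). Period 1 is double-blind, so an ambiguous form would mainly add noise in all arms. This limits the weight of the point but does not reconcile the two definitions.

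**Conclusion.** The textual defect is certain. Protocol 7.1.4 double-grades 1 to 4 inflammatory nodules alone on its natural reading, and on every reading tried it gives no grade to 5 or more with no abscess and no draining fistula. The SAP table has neither fault. The SAP's gap is one of linkage: it analyses the CRF score without saying which definition the form carries, without a derivation, and without listing the changed definition in Section X.

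The consequence is conditional. If the form or the sites used the protocol wording, baseline HS-PGA and change in HS-PGA could be misclassified for these patterns, in an unknown number of subjects. If the form carried the SAP wording, the recorded scores rest on a sound definition and only the documentation needs correcting. Neither case touches the primary endpoint or the ranked secondary endpoints, none of which uses HS-PGA.

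**What to change.** 1. Correct Protocol 7.1.4 to match the SAP table. This aligns the documents but does not change any grade already recorded.
2. State in SAP VIII.B which definition the HS-PGA CRF carried, and list the changed definition in SAP Section X.
3. Derive HS-PGA by program from the inflammatory nodule, non-inflammatory nodule, abscess and draining fistula counts at each visit, using the SAP table, and list discrepancies with the CRF score. Say how the rule that treated lesions count as permanently present (SAP VIII.C) enters the derivation, since it could itself cause discrepancies.
4. Report the derived score as a sensitivity analysis. Make it the main HS-PGA analysis if the CRF carried the protocol wording.

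The cost is a text correction, two SAP entries and a small amount of extra programming. The needed counts are already in the SAP's own analyses, so no new data collection is involved.

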7.1.5. Global Assessment of Skin Pain

Subjects will record the maximum severity pain on a numeric rating scale from 0 (no skin pain) to 10 (skin pain as bad as can be imagined) in a daily diary from one week prior to Day 1 through the Week 44 visit.

The weekly average of the maximum severity pain for visits designated in the [Time and Events Table](#) will be calculated programmatically.

7.1.6. Health-Related Quality of Life Assessments

The SF-36 v2 and EQ-5D-5L instruments are widely accepted global non-disease-specific tools to measure changes in subjects' health-related quality of life. The HiSQOL index (an HS-specific instrument) and DLQI instruments are designed to measure the impact of HS or skin disease on subjects' quality of life. Forms for these instruments will be completed by study subjects at visits specified in the [Time and Events Table](#). Proven translations will be used for non-English speaking subjects, whenever possible.

Study site personnel will facilitate completion of the questionnaires by the subjects, but will not complete the forms for the subjects. The administrator will establish a rapport with the subject, emphasize the importance of completing the form, and serve to answer questions and address concerns. Subjects should complete the questionnaires before seeing the Investigator at the visit.

7.1.7. Health-Economic Information

The WPAI:SHP (<https://www.cdisc.org/foundational/qrs>) assesses the effect of general and specific health conditions on productivity losses. Scores are calculated for four areas: percent work time missed due to HS, percent impairment while working due to HS, percent overall work impairment due to HS, and percent activity impairment due to HS. Forms for this instrument will be completed by study subjects at visits specified in the [Time and Events Table](#) to measure changes from baseline in work productivity and activity impairment.

Other health-economic information will be recorded by the study personnel on the appropriate CRFs such as details on Hospitalizations (i.e., Number of Hospitalizations total and due to HS, Number of days hospitalized, Number of days missed from work), Emergency or Urgent Care visit (i.e., Number of visits total and due to HS, Number of days (or hours where applicable) missed from work), Lesion interventions for HS (i.e., Number of days (or hours where applicable) missed from work due to HS lesion interventions).

